All subjects aged 12 years and older, with at least 365 days of data availability before index date (ID) [ID defined as the date of the latest vaccine dose administered] AND data availability from 12/2020 onwards (i.e. the time when the roll-out of the vaccination campaign started) in the respective database will be included.

	Phase II C3-002 – Study Protocol							
	Author(s): [name], [name], [name]				Version: v2.1			
	Dissemination level: Public							

All studies will be carried out comparing the following cohorts, which we defined based on varying degrees of vaccine exposure and period of predominant SARS-CoV-2 variant as shown in Table 1 below.

COVID-19 vaccination history	Cohort number							
	1	2	3	4	5	6	7	8
1 dose only					x			
Complete primary vaccination course (monovalent only)	x	x	x	x		x	x	x
3rd dose, also called 1st booster (monovalent or any of the adapted, bivalent)	x	x	x	x			x	x
4th dose, also called 2nd booster (monovalent or any of the adapted, bivalent)		x						x
4th dose, also called 2nd booster (any of the monovalent)			x					
4th dose, also called 2nd booster (any of the adapted, bivalent boosters)				x				
Study period								
Start of roll-out 4 th dose/2 nd booster onwards	x	x	x	x				
XBB variant or later dominant	x	x	x	x				
Any variant dominant					x	x	x	x

*Cohorts 3 and 4 will only be created for databases where the vaccine product is reliably recorded in addition to vaccine brand.

Outcomes 1-2 will be assessed in cohorts 1-2 (and 3-4 where available), outcomes 3-7 will be assessed in cohorts 5-8.

Unvaccinated groups will not be used as a comparator in our study for vaccine effectiveness research because they may be very different from vaccinated individuals regarding their risk of infection with SARS-Cov-2. This study therefore focusses on the association of varying degrees of vaccine exposure and COVID-19 related outcomes.

Study period:

Period of “start of roll-out 4th dose/2nd booster dose onwards”: from 01/08/2022 - last available data for each database.

Period of “XBB variant or later dominant”: 01/03/2023 - last available data for each database. Note: This period is not covered by any of the data cuts onboarded for DARWIN EU at the time of protocol submission.

Period of “any variant dominant”: 01/01/2021 (when the wider roll-out of the vaccination campaign started) - last available data for each database.

Statistical analyses:

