Hazard ratios will be calculated for subsequent time windows after index date, i.e. in bi-weekly intervals.

Monthly intervals will be used in case of small event counts to increase sample size and power if needed.

Kaplan-Meier plots and/or cumulative incidence plots will be used to illustrate survival analyses.

Objectives 3-6: Post-acute COVID-19 complications

The following comparisons will be conducted for objectives 3-6:

- First-dose vaccinated vs. second-dose vaccinated [cohort 5 vs. 6]
- Second-dose vaccinated vs. 3rd dose vaccinated (1st booster dose) [cohort 6 vs 7]
- 3rd dose vaccinated vs. 4th dose vaccinated (2nd booster dose) [cohort 7 vs 8]

Objective 3 will be assessed for SIDIAP and IPCI only, whereas objectives 4-6 will be assessed in CPRD, IPCI and SIDIAP.

Study population

The study populations will be derived similar to the inclusion process outlined for objectives 1-2 above, including sequential matching.

For objectives 4 and 5, people with the respective outcome recorded anytime in their history will be excluded for the respective objective. For objective 6, an outcome-free washout window of 365 days prior to index date will be implemented.

Outcomes:

- COVID-19 hospitalization + death within 3/6 months from discharge
- SARS-CoV-2 infection + New onset diabetes Type 1 diabetes within 30-365 days after COVID-19
- SARS-CoV-2 infection + New onset diabetes Type 2 diabetes within 30-365 days after COVID-19
- SARS-CoV-2 infection + cardiovascular events (ccar) in the 12 months after a SARS-CoV-2 infection

	Phase II C3-002 – Study Protocol	
	Author(s): [name], [name], [name]	Version: v2.1
		Dissemination level: Public

For contextualization and interpretation of the study findings, we will also report the number of people with COVID-19 hospitalization and SARS-CoV-2 infections in each group, as these are part of the overall outcomes of “death following discharge from COVID-19 hospitalisation” and post COVID-19 complications.

Vaccine effectiveness analyses for COVID-19 related mortality following hospital discharge:

Incidence rates will be calculated for the matched cohorts and outcome. Cox proportional hazard models will be calculated for each outcome to provide HR. Negative control outcomes will be used as an additional measure to measure residual confounding. In the scenario of potential unmeasured confounding being detected by NCO, empirical calibration²⁵ for HR might be considered to minimise bias.

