8.4 Follow-up

For all analyses, follow-up time will start from index date.

End of follow-up for each objective will be the end of a person’s observation time (i.e. date of data extraction, database availability or death), the date of their next vaccine dose, fixed duration or the date of the respective outcome event, whatever comes first

Table 8.4.1: Operational Definition of Time 0 (index date) and other primary time anchors

Study population name(s)	Time Anchor Description (e.g. time 0)	Number of entries	Type of entry	Washout window	Care Setting ¹	Code Type	Diagnosis position	Incident with respect to...	Measurement characteristics/ validation	Source of algorithm
1 dose only	Vaccination date 1 st dose	1	incident	All history	OP	RxNorm	n/a	vaccination	n/a	n/a
Complete primary vaccination course (2 doses)	Vaccination date 2 nd dose	1	n/a	21days	OP	RxNorm	n/a	n/a	n/a	n/a
3rd dose (monovalent or adapted/bivalent)	Vaccination date 3 rd dose	1	n/a	90days	OP	RxNorm	n/a	n/a	n/a	n/a
4th dose (monovalent or adapted/bivalent)	Vaccination date 4 th dose	1	n/a	90days	OP	RxNorm	n/a	n/a	n/a	n/a
4th dose (any monovalent)	Vaccination date 4 th dose	1	n/a	90days	OP	RxNorm	n/a	n/a	n/a	n/a
4th dose, (any adapted/bivalent boosters)	Vaccination date 4 th dose	1	n/a	90days	OP	RxNorm	n/a	n/a	n/a	n/a

OP = outpatient, n/a = not applicable

	Phase II C3-002 – Study Protocol	
	Author(s): [name], [name], [name]	Version: v2
		Dissemination level: Public

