8.5 Study Population with inclusion and exclusion criteria

The source population will comprise all subjects aged 12 years and older, with at least 365 days of data availability in the respective database before index date (ID) [ID defined as the date of the “latest” vaccine dose administered] AND data availability from 12/2020 onwards (i.e. the time when the roll-out of the vaccination campaign started) in the respective database will be included.

People will then be matched 1:1 based on the number of vaccines doses they received [exposure], with their matched counterparts having 1 vaccine dose less at the time of matching. Based on the index date of matched counterparts, the following inclusion criteria will be applied:

- At least 365 days of data availability in the respective database
- At least 90days of time elapsed since the last vaccine dose for >2 doses), at least 21days of time elapsed since the last vaccine dose for 2 doses and no previous vaccine dose recorded for 1st dose).
- At least 90days of time elapsed since the last record of a clinical diagnosis of COVID-19 or positive SARS-COV-2 test.

For analyses where diabetes mellitus or cardiovascular events are assessed as post-acute COVID-19 complications, people must not have had a record of the outcome within 365days before their index date for cardiovascular events, and no record anytime before index date for diabetes.

Operational definitions of Inclusion and Exclusion Criteria are provided in [Tables 8.5.1](#) and [8.5.2](#).

	Phase II C3-002 – Study Protocol	
	Author(s): [name], [name], [name]	Version: v2
	Dissemination level: Public	

Table 8.5.1. Operational Definitions of Inclusion Criteria

Criterion	Details	Order of application	Assessment window	Care Settings ¹	Code Type	Diagnosis position ²	Applied to study populations:	Measurement characteristics/validation	Source for algorithm
Observation period of 365day prior entry (all cohorts)	Study participants will be required to have 365 days prior history observed before contributing observation time	before	[-365, 0]	n/a	n/a	n/a	All individuals within the selected databases	n/a	n/a
Covid-19 vaccinated: 1 dose only	Exactly 1 Comirnaty/Spikevax vaccination record	after	n/a	OP	RxNorm	n/a			
Covid-19 vaccinated: Completed primary vaccination course	Exactly 2 vaccination records, with the latest being Comirnaty/Spikevax and at least 21days later than the 1st dose.								

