8.8.3 Objectives 1-2: Vaccine effectiveness to prevent severe infection

Objectives 1 and 2 will assess the effectiveness of a 4th COVID-19 vaccine dose in people with 3 vaccine doses.

Study population

All people with a 3rd vaccine dose of Comirnaty or Spikevax will be included from the source population. Cohorts will be generated separately for Comirnaty and Spikevax, respectively.

Study inclusion: Sequential matching

Inclusion will be conducted using a sequential matching design, with similar designs being used in previous studies assessing vaccine effectiveness. Previous research showed matching to adequately reduce measured confounding in vaccine effectiveness research when including key variables such as geographic location²⁴.

Matching process using key confounders and Propensity Scores

For each calendar week starting from the day when a 4th vaccine dose (i.e. 2nd booster vaccine) became available/recommended in the respective country, people will be assigned to two cohorts: people who received a 4th vaccine dose during that week and people who did not receive a 4th dose.

Using the first day of the respective week as “preliminary” index date for non-boostered people, and the date of the 4th dose for booster-vaccinated people, the following inclusion criteria will be applied:

	Phase II C3-002 – Study Protocol	
	Author(s): [name], [name], [name]	Version: v2.1
		Dissemination level: Public

- At least 365 days of data availability in the respective database
- At least 90days of time elapsed since the previous vaccine dose (i.e. the 3rd or 4th vaccine dose)
- At least 90days of time elapsed since the last record of a clinical diagnosis of COVID-19 or positive SARS-COV-2 test.

Among those people in the cohorts who received or not received a 4th dose and met the inclusion criteria, non-boostered people will be matched 1:1 to a person receiving their 4th dose, based on key confounders and large-scale propensity scores using nearest neighbor matching, with caliper width 0.2 standard deviation. Key confounders will comprise but are not limited to:

- Age (e.g. 5-year age bands)
- Sex (exact)
- Geographic location (exact)
- Previous vaccine brands (e.g. homologous or heterologous vaccination scheme)
- Time from previous vaccination
- History of conditions for prioritization for vaccination
- immunocompromised status
- previous SARS-CoV-2 diagnosis (>90days before index date)

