Large-scale propensity scores (PS) will be computed to estimate the probability of receiving a 4th vaccine dose. Covariates to be included in the large-scale PS will be selected from co-medications and comorbidities recorded prior to cohort-specific index dates. Among those, covariates with a prevalence below 0.5% in the study population will be omitted. Logistic regression with LASSO regularization will then be used for variable selection. The list of selected covariates will be manually screened by 2 epidemiologists/clinical domain experts to exclude potential instrumental variables.

The same procedure will be conducted in the calendar week after, with previously non-boostered people being allowed to be included in the booster cohort once they change exposure status. Non-boostered people can only be matched once to a booster counterpart during the whole study. With matching, non-boostered counterparts will be assigned the date of when the booster counterpart received their 4th vaccine dose as their “final” index date (index date for the matched pair).

All booster and matched non-boostered people from sequential weekly matching will be combined into the booster and non-boostered cohort for subsequent analyses. The study inclusion and sequential matching process is illustrated in [Figure 8.8.3.1](#) below.

[figure not shown]

	Phase II C3-002 – Study Protocol	
	Author(s): [name], [name], [name]	Version: v2.1
	Dissemination level: Public	

Figure 8.8.3.1 Study inclusion and sequential matching process

	Phase II C3-002 – Study Protocol	
	Author(s): [name], [name], [name]	Version: v2.1
		Dissemination level: Public

Follow-up

In the matched cohorts, people will be followed up from their index date until the earliest of

- End of their observation (i.e. date of data extraction, death)
- 2nd booster vaccination for unvaccinated group, 3rd booster for vaccinated group etc.
- COVID-19 related hospitalization or death, with outcome date being defined as the date of first COVID-19 diagnosis/positive test related to hospitalization or death.

Follow-up will be censored for the matched pair if one counterpart is censored, but not if one counterpart experiences the outcome.

Outcomes

The outcomes are defined in detail in section 8.6.2.

COVID-19 related hospitalization will be assessed for SIDIAP and IPCI. COVID-19 related death will be assessed for CPRD, IPCI and SIDIAP.

Statistical Analyses

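### Time zero is each person's own last dose in Table 8.4.1 and the index-date definition but the matched partner's dose date in 8.8.3 to 8.8.5, and 8.8.3 checks comparator eligibility up to 6 days before that date

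*Protocol*

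**What the plan says.** **Time zero.** Section 8.4 states: "For all analyses, follow-up time will start from index date". The table beneath it, headed "Table 8.4.1: Operational Definition of Time 0 (index date) and other primary time anchors", has one row per dose level, each anchored at that population's own dose. The one-dose row reads "Vaccination date 1 st dose". The abstract defines the source population with "ID defined as the date of the latest vaccine dose administered", and 8.5 repeats this definition.

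Section 8.8.3 sets a different date for pairs: "non-boostered counterparts will be assigned the date of when the booster counterpart received their 4th vaccine dose". The abstract says the same. Sections 8.8.4 and 8.8.5 start follow-up on the date of the new dose for the matched pair. Table 7.1 starts it at the index date of the matched people.

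**Eligibility date.** Section 8.8.3 uses the first day of the calendar week as preliminary "index date for non-boostered people, and the date of the 4th dose for booster-vaccinated people, the following inclusion criteria will be applied". It also sorts people into boosted and non-boosted by what happens during the whole week. Section 8.5 says: "Based on the index date of matched counterparts, the following inclusion criteria will be applied". Table 8.5.2 requires no COVID-19 record in the 90 days up to the index date, for the whole study population.

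**The concern.** In a sequentially matched cohort, three things should coincide for both pair members: the date eligibility is judged, the date exposure status is judged, and the date the clock starts. Here the text gives the comparator three candidate dates: its own last dose, the first day of the week, and the partner's dose date.

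Two separate problems follow, and they do not add up because they belong to different readings.

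- If a programmer takes time zero for comparators from Table 8.4.1, their clock starts before matching. That time is event-free by construction, because they had to stay eligible in order to be matched. The comparator rate is diluted and effectiveness is understated.
- If 8.8.3 is followed, the clocks agree but the eligibility checks do not. The comparator can be checked up to 6 days earlier than its partner, and 8.8.3 does not repeat the check once the final index date is known.

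One study package runs in all databases (8.8), so either choice reaches every estimate. Section 8.8.6 plans no sensitivity analysis that would show the difference.

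**Working it through.** The protocol gives no sample size, event count or effect target, so there is no planned figure to reproduce. The check compares the passages and then sizes each consequence under stated assumptions.

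**Step 1. Can Table 8.4.1 be read as describing only newly dosed groups?** Mostly yes. The two-, three- and four-dose rows each describe a group that is the newly dosed arm in some comparison (cohort 6 in 5 vs 6, cohort 7 in 6 vs 7, cohort 8 in 7 vs 8, and cohorts 2 to 4). The one-dose row has no such role, because cohort 5 appears only as comparator to cohort 6. Its time zero in the table is therefore a comparator's own last dose.

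The own-dose date also carries into eligibility. Section 8.5 and Table 8.5.2 require no previous COVID-19 vaccination up to the index date for first-dose people. On a pair date, which is the partner's second dose, every cohort 5 comparator already has a recorded dose and would fail. The rule works only with an own-dose index date.

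**Step 2. What the literal table reading would do.** Let G be the event-free days before matching and F the days followed after matching. With no true effect, the crude rate ratio (newly dosed over comparator) becomes (F + G)/F. G is at least 90 days for third and fourth doses and 21 days for the second dose (8.5, 8.8.4). F is an assumption.

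| G | F | (F + G)/F | True effectiveness of 50% appears as |
|---|---|---|---|
| 90 | 90 | 180/90 = 2.0 | 1 − 0.5 × 2.0 = 0% |
| 90 | 180 | 270/180 = 1.5 | 1 − 0.5 × 1.5 = 25% |
| 21 | 90 | 111/90 = 1.23 | 1 − 0.5 × 1.23 = 38% |
| 21 | 180 | 201/180 = 1.12 | 1 − 0.5 × 1.12 = 44% |

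The crude ratio shows direction, not the size a Cox model would give. A small simulation used 6,000 pairs, 180 days of follow-up, an assumed hazard of 0.0005 per day, gaps of 90 to 209 days treated as wholly event-free, and three runs per setting.

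- Own-dose clock for comparators: hazard ratios of 4.98 to 5.86 for a true value of 1, and 2.51 to 3.23 for a true value of 0.5.
- Pair date for both members: 0.88 to 1.08 and 0.47 to 0.55.

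**Step 3. What 8.8.3 does as written.** The comparator is checked 0 to 6 days before its final index date. If doses are spread evenly over the week, the mean is (0 + 1 + … + 6)/7 = 3 days. With weekly recorded infection risk w, the share newly failing the 90-day COVID-19 rule after d days is 1 − (1 − w)^(d/7). The values of w are assumptions.

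| w | Mean gap, d = 3 | Maximum gap, d = 6 |
|---|---|---|
| 0.1% | 0.04% | 0.09% |
| 0.5% | 0.22% | 0.43% |
| 1% | 0.43% | 0.86% |
| 2% | 0.86% | 1.7% |

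The requirements on prior data and time since last dose cannot be newly failed by waiting. The COVID-19 rule can, and so can being alive and under observation.

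**Step 4. Outcome dates.** Section 8.8.3 dates an outcome at the first related diagnosis or positive test, and 8.6.2 allows that test up to 21 days before admission. A comparator who tests positive between the week-start check and the pair date, and is then admitted, has an outcome dated before time zero. Section 8.8.3 does not say what happens to it. Counting it adds early comparator events and dropping it does not, so the protocol does not fix the sign of the bias.

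**The case against.** The strongest reply is that the protocol does fix one time zero for pairs and repeats it in the abstract, 8.8.3, 8.8.4 and 8.8.5, with Table 7.1 in agreement. The own-dose definition sits in the source-population sentence, before matching. Table 8.4.1 also announces other time anchors besides time zero. This stands: the pair date is the dominant rule. A reader might infer from Table 8.4.1 that the planned estimates contain immortal time, but the documents do not support that, because it needs the table to override four other places. Nor does the week-start check create immortal time, since both members still start on the same date.

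A reader might also extend the one-dose argument to the three-dose comparators of Objectives 1 and 2. That is weak, because the three-dose row also serves cohort 7, a newly dosed arm.

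On eligibility, the reply is that the week start is called preliminary and that 8.5 and Table 8.5.2 already tie the COVID-19 rule to the index date. This stands in part. If the index date there means the pair date, the recheck is implied. But 8.5 itself defines the index date as the latest dose, and 8.8.3 assigns the final date without saying the criteria are applied again.

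Finally, a large bias could be derived by counting pre-index infections as events. The protocol does not say they are counted, and follow-up runs from the index date, so no such figure is supported.

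**Conclusion.** The inconsistency is real and needs correcting, but its likely effect is modest. The own-dose date in Table 8.4.1 and the index-date definition conflicts with the pair date used everywhere the analysis is described, and the one-dose row cannot be explained as a newly dosed group. Only a literal use of that table for comparators would understate effectiveness. Under the pair date this bias is absent.

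What remains under 8.8.3 as written is an eligibility difference of at most 6 days. It touches on average about 0.04% to 0.86% of comparators, assuming evenly spread doses and a weekly recorded infection risk of 0.1% to 2%, neither of which the protocol states. Any effect falls mainly in the first two-week window of Objective 2. The share of comparators affected is small. The direction of the effect depends on how outcomes dated before time zero are handled, which is not stated. Classifying people as non-boosted over the whole week also uses information from after the pair date.

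**What to change.** - In 8.4, Table 8.4.1, 8.5 and the abstract, state that time zero for both pair members is the dose date of the higher-dose member.
- In 8.8.3, describe the week-start check as screening only. After matching, re-apply the existing inclusion criteria to both members on the pair date, together with the comparator's dose count and being alive and under observation. Drop or re-match pairs that fail.
- Judge non-boosted status on the pair date, not over the calendar week.
- For cohort 5, express the no-previous-vaccination rule as exactly one recorded dose by the pair date. Otherwise the recheck would remove every one-dose comparator.

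The recheck also removes outcomes dated before time zero. The cost is protocol wording and one filter in the matching code. The downside is that a few pairs are lost or re-matched.

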8.5 Study Population with inclusion and exclusion criteria

The source population will comprise all subjects aged 12 years and older, with at least 365 days of data availability in the respective database before index date (ID) [ID defined as the date of the “latest” vaccine dose administered] AND data availability from 12/2020 onwards (i.e. the time when the roll-out of the vaccination campaign started) in the respective database will be included.

People will then be matched 1:1 based on the number of vaccines doses they received [exposure], with their matched counterparts having 1 vaccine dose less at the time of matching. Based on the index date of matched counterparts, the following inclusion criteria will be applied:

- At least 365 days of data availability in the respective database
- At least 90days of time elapsed since the last vaccine dose for >2 doses), at least 21days of time elapsed since the last vaccine dose for 2 doses and no previous vaccine dose recorded for 1st dose).
- At least 90days of time elapsed since the last record of a clinical diagnosis of COVID-19 or positive SARS-COV-2 test.

For analyses where diabetes mellitus or cardiovascular events are assessed as post-acute COVID-19 complications, people must not have had a record of the outcome within 365days before their index date for cardiovascular events, and no record anytime before index date for diabetes.

Operational definitions of Inclusion and Exclusion Criteria are provided in [Tables 8.5.1](#) and [8.5.2](#).

	Phase II C3-002 – Study Protocol	
	Author(s): [name], [name], [name]	Version: v2
	Dissemination level: Public	

Table 8.5.1. Operational Definitions of Inclusion Criteria

Criterion	Details	Order of application	Assessment window	Care Settings ¹	Code Type	Diagnosis position ²	Applied to study populations:	Measurement characteristics/validation	Source for algorithm
Observation period of 365day prior entry (all cohorts)	Study participants will be required to have 365 days prior history observed before contributing observation time	before	[-365, 0]	n/a	n/a	n/a	All individuals within the selected databases	n/a	n/a
Covid-19 vaccinated: 1 dose only	Exactly 1 Comirnaty/Spikevax vaccination record	after	n/a	OP	RxNorm	n/a			
Covid-19 vaccinated: Completed primary vaccination course	Exactly 2 vaccination records, with the latest being Comirnaty/Spikevax and at least 21days later than the 1st dose.								
Covid-19 vaccinated: 3 rd dose	Exactly 3 vaccination records, with the 3 rd dose being either monovalent or any of the adapted, bivalent Comirnaty/Spikevax vaccines								
Covid-19 vaccinated: 4 th dose, monovalent or adapted/bivalent	Exactly 4 vaccination records, with the latest being Comirnaty/Spikevax								
Covid-19 vaccinated: 4 th dose, monovalent	Exactly 4 vaccination records, with the 4 rd dose being a monovalent Comirnaty/Spikevax vaccine								
Covid-19 vaccinated: 4 th dose, adapted/bivalent	Exactly 4 vaccination records, with the 4 rd dose being any of the adapted, bivalent Comirnaty/Spikevax vaccines								

OP = outpatient, n/a = not applicable

	Phase II C3-002 – Study Protocol	
	Author(s): [name], [name], [name]	Version: v2.1
	Dissemination level: Public	

Table 8.5.2. Operational Definitions of Exclusion Criteria

Criterion	Details	Order of application	Assessment window	Care Settings ¹	Code Type	Diagnosis position ²	Applied to study populations:	Measurement characteristics/validation	Source for algorithm
At least 90days of time elapsed since the last vaccine dose at the time of study inclusion [3rd, 4 th dose]	Study participants will be required to have at least 90days of time elapsed between their 2 nd and 3 rd , or 3 rd and 4 th vaccine dose.	after	[-90, ID]	OP	RxNorm	n/a	People with 3 rd and 4 th vaccine dose	n/a	n/a
At least 21days of time elapsed since the last vaccine dose at the time of study inclusion. [2 nd dose]	Study participants will be required to have at least 21days of time elapsed between their 2 nd and 1 st , vaccine dose.	after	[-21, ID]	OP	RxNorm	n/a	People with 2 nd vaccine dose	n/a	n/a
No record of a previous COVID-19 vaccination [1 st dose]	Study participants will be required to have no record of a previous COVID-19 vaccination	after	[- anytime, ID]	OP	RxNorm	n/a	People with 1 st vaccine dose	n/a	n/a
At least 90days of time elapsed since the last record of a clinical diagnosis of COVID-19 or positive SARS-COV-2 test at the time of study inclusion	Study participants will be required to have no record of a clinical diagnosis of COVID-19 or positive SARS-COV-2 test within 90days before their index date	after	[-90, ID]	OP	SNOMED	n/a	All study population	n/a	n/a
No diagnosis of the respective outcome in the patient's history [Objectives 4, 5]	Patients included for analyses in objectives 4 and 5 will be excluded if they have the respective outcome of interest (diabetes) recorded in their patient history any time prior to index date	after	[- anytime, ID]	OP	SNOMEDRXNorm	n/a	Patients included for objectives 4 and 5	n/a	n/a
No diagnosis of the respective outcome in the patient's history [Objectives 4, 5]	Patients included for analyses in objective 6 will be excluded if they have the respective outcome of interest (cardiovascular conditions) recorded within the 365days before index date	after	[-365, ID]	OP	SNOMED	n/a	Patients included for objective 6	n/a	n/a

ID = index date, OP = outpatient, n/a = not applicable

	Phase II C3-002 – Study Protocol	
	Author(s): [name], [name], [name]	Version: v2
		Dissemination level: Public

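### For 2-versus-3 and 1-versus-2 dose pairs, section 8.5 and Table 8.5.2 set the minimum time since last dose by each person's own dose count, so partners face different rules, and other sections disagree

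*Protocol*

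**What the plan says.** Section 8.5 of the protocol matches people 1:1 on number of doses, "with their matched counterparts having 1 vaccine dose less at the time of matching". It then fixes the timing: "Based on the index date of matched counterparts, the following inclusion criteria will be applied". The interval criterion has three parts: "At least 90days of time elapsed since the last vaccine dose for >2 doses", followed by "at least 21days of time elapsed since the last vaccine dose for 2 doses and no previous vaccine dose recorded for 1st dose".

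Table 8.5.2 turns this into three rows, applied respectively to people with a 3rd or 4th dose, people with a 2nd dose and people with a 1st dose. The row titles speak of time since the last dose at study inclusion, but the details column measures something else:
- 3rd and 4th dose: "at least 90days of time elapsed between their 2 nd and 3 rd , or 3 rd and 4 th vaccine dose"
- 2nd dose: "at least 21days of time elapsed between their 2 nd and 1 st , vaccine dose"
- 1st dose: "Study participants will be required to have no record of a previous COVID-19 vaccination"

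Other sections differ. Table 7.1, parts B and C (Objectives 3-6), asks for 90 days since the last dose from everyone and has no 21-day rule. Section 8.8.4 gives 90 days for the 3rd or 4th dose and 21 days for the 2nd, and 8.8.5 adopts those criteria for Objectives 4-6. Section 8.8.3 (Objectives 1-2) applies one list to both groups: "At least 90days of time elapsed since the previous vaccine dose (i.e. the 3rd or 4th vaccine dose").

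**The concern.** In a sequentially matched design, both members of a pair should be eligible for the new dose on the index date, and differ only in whether they received it. A minimum time since the previous dose is part of that eligibility. If it depends on how many doses a person already holds, it changes within the pair, because the partners differ by one dose by construction.

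The comparison most exposed is 2 versus 3 doses in Objectives 3-6. A comparator 25 days after dose 2 could sit opposite someone who was at least 90 days past dose 2 when dose 3 was given. The comparator would be nearer the last dose, and the contrast would no longer be adding a dose versus not adding one at the same point in the schedule.

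Because the sections also disagree, two programmers could build different eligible populations from the same protocol.

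**Working it through.** The protocol has no figure of its own to reproduce here, so the check lists the minimum time since dose n-1 that each partner must have at the pair's index date.

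**Which date.** Section 8.8.3 gives the comparator the partner's vaccination date as final index date. Sections 8.8.4 and 8.8.5 start follow-up at the new dose for matched pairs.

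**Whose dose count.** The abstract rules out unvaccinated comparators, and the only comparisons are 1 versus 2, 2 versus 3 and 3 versus 4. One-dose people are therefore only ever comparators. A clause for the 1st dose has a function only if the list in 8.5 follows each person's own dose number, comparators included. The applied-to column of Table 8.5.2 says the same.

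**Results** (newly dosed person / comparator, in days):

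| Comparison | 8.5, own dose count | 8.8.4 read per comparison | Table 7.1 |
|---|---|---|---|
| 1 vs 2 | 21 / no minimum | 21 / 21 | 90 / 90 |
| 2 vs 3 | 90 / 21 | 90 / 90 | 90 / 90 |
| 3 vs 4 | 90 / 90 | 90 / 90 | 90 / 90 |

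**Gap for 2 versus 3.** Under 8.5: 90 - 21 = 69 days. Under the details column of Table 8.5.2, the comparator's 21 days run from dose 1 to dose 2, so nothing is required after dose 2 and the gap is up to 90 - 0 = 90 days.

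**3 versus 4.** Section 8.5, Table 7.1, 8.8.4 and, for Objectives 1-2, 8.8.3 all give 90 days. No gap arises.

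**Consistency.** For 1 versus 2 the three columns give three different rules. For 2 versus 3, 8.5 stands against the other two. No section is said to take precedence.

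**The case against.** The strongest reply is that 8.8.4 is the operative text for Objectives 3-6 and reads naturally as one interval per dose under evaluation. It derives its populations in the manner of Objectives 1-2, where one rule covers both arms. Table 7.1 is also symmetric. This stands as a possible reading, and it limits the point: the protocol contradicts itself rather than clearly choosing an asymmetric design. It does not remove the point, since 8.5 and Table 8.5.2 are the formal eligibility definitions.

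Second, time since the previous vaccination is a listed matching variable. Close matching would keep a comparator at 25 days away from a partner at 90 or more. That stands too, and the tolerance may properly be left to the analysis plan. But none is stated here, and a matching variable does not make the eligibility rules equal.

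Two stronger readings are tempting and should not be adopted:
- **An empty 1-dose arm.** The 1st-dose row has a window running up to the index date, so a reader might infer that each 1-dose comparator's own first dose excludes them. Table 8.4.1 anchors that cohort at its first dose with an all-history washout, and Table 8.5.1 requires exactly one record. The row is therefore best read as no vaccination before that first dose. The same literalism would also exclude every 3rd-dose person, whose new dose falls on the last day of the 90-day window.
- **A gap for 3-dose comparators.** Table 8.5.2's details column, taken alone, looks only at doses 2 to 3. Its row title and the other sections require 90 days since the last dose.

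**Conclusion.** The point holds for 2 versus 3 doses in Objectives 3-6, and to a lesser degree for 1 versus 2. As written in 8.5 and Table 8.5.2, partners face minimum intervals of 90 against 21 days (or none), and 21 days against none. This conflicts with Table 7.1 and with a natural reading of 8.8.4. Objectives 1-2 and 3-versus-4 pairs are not materially affected.

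For 2 versus 3, the likely direction is towards the null, on two assumptions: that protection is higher soon after dose 2 than 90 or more days later, and that matching leaves some recently dosed comparators in place. A reader might go further and infer a definite loss of estimated vaccine effectiveness. The documents do not support a figure, because they give neither hazards by time since dose nor the share of recently dosed comparators. For 1 versus 2, no direction is shown: the newly dosed person needs only 21 days, and nothing in the documents describes protection shortly after a first dose.

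This should be corrected before cohorts are built, as a contradiction in eligibility with a possible bias attached.

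**What to change.** Reconcile 8.5, Table 8.5.2, 8.8.4 and Table 7.1 so that each comparison of n-1 versus n doses has one minimum interval. It should apply equally to the newly dosed person and the comparator, and be measured from dose n-1 to the pair's index date. The sponsor must settle the values; this point favours neither 21 nor 90 days.

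Suggested wording: at the pair's index date, both members must have at least the interval specified for this comparison since dose n-1.

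Reword the 1st-dose row of Table 8.5.2 as no vaccination before the person's own first dose, and exactly one dose recorded before the pair's index date. Bring the details column for the 2nd, 3rd and 4th doses into line with the row titles.

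The cost is rewording in four places and one filter in the matching code. Some recently dosed comparators will be lost.
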